3.2 Blinding and Randomization Methods

All subjects receive KRN23 on an open-label basis. Blinding and randomization are not applicable to this study design.

3.3 Stratification Factors

Not applicable.

3.4 Determination of Sample Size

The study will enroll approximately 14 adult subjects with XLH; baseline histologic and histomorphometric assessments of the bone biopsy specimens will be performed as each biopsy is completed to assess sample quality and confirm the presence of osteomalacia in at least 8 subjects. To ensure a level of gender balance, at least 3 subjects of each sex will be enrolled. At least 6 paired biopsy specimens are expected at the end of the study. A reduction in excess osteoid is expected to be shown in all subjects with paired biopsies with an estimated [REDACTED] reduction from baseline in osteoid thickness. The sample size and study duration are believed to be sufficient to enable characterization of KRN23 effects on bone tissue and skeletal health.

Information will be used to support the findings of UX023-CL303 study which is a larger Phase 3 confirmatory efficacy and safety study, where it is adequately powered to evaluate increases in serum phosphorus levels across the entire dosing interval and to describe the treatment effect on select patient reported outcomes.

3.5 Primary and Final Analyses

The primary efficacy analysis will be performed after all subjects have completed Week 48 or discontinued from the study prior to week 48 and completed the post-baseline Bone Biopsy test for those who has been determined to have the osteomalacia at the baseline.

The final analysis will be performed after all subjects have completed the Week 96 assessments and the Safety Follow-up or discontinued from the study.

Administrative analyses during the Open Label Treatment Period and Treatment Extension Periods may be performed to support regulatory activities.

3.6 Data Monitoring Committee

An independent DMC that includes two clinicians with expertise in metabolic bone disease and one statistician will act in an advisory capacity to monitor subject safety on a routine basis throughout the trial. A review of safety data will be conducted by the DMC periodically. Ad hoc meetings will be held if indicated based on observed events. The roles and responsibilities of the DMC will be defined in the DMC Charter.

4 STUDY CLINICAL OUTCOMES AND COVARIATES

4.1 Primary Efficacy Endpoint

The primary endpoint is the percent change from baseline in osteoid volume/bone volume (OV/BV) at Week 48 based on analysis of iliac crest bone biopsies

4.2 Key Secondary Efficacy Endpoint

The key secondary efficacy endpoint is the proportion of subjects achieving mean serum phosphorus levels above the lower limit of normal (LLN; 2.5 mg/dL [0.81 mmol/L]) at the mid-point of the dose interval (i.e., Weeks 2, 6, 14, and 22), as averaged across dose cycles between baseline and Week 24.

4.3 Secondary Efficacy Endpoints

The secondary efficacy endpoints will compare the effects of treatment with KRN23 on the following:

- Percent changes from baseline in additional histomorphometric parameters – including osteoid thickness (O.Th), osteoid surface/bone surface (OS/BS), and mineralization lag time (MLt) at Week 48
- Changes from baseline in MAR, MS/BS, BFR and additional measures of bone formation and remodeling at Week 48
- Additional measures to assess serum phosphorus levels between baseline and Week 24 include:
 - Proportion of subjects achieving mean serum phosphorus levels above the LLN (2.5 mg/dL [0.81 mmol/L]) at the end of the dosing cycle (4 weeks after dosing), as averaged across dose cycles
 - Mid-point of dosing cycle: mean change from baseline, and percent change from baseline averaged across dose cycles
 - End of dosing cycle: mean change from baseline, and percent change from baseline averaged across dose cycles
 - Cumulative exposure: time-adjusted area under the curve (AUC)
- Change from baseline over time in serum phosphorus, serum intact FGF23, serum 1,25(OH)₂D, urinary phosphorus, ratio of renal tubular maximum reabsorption rate of phosphate to glomerular filtration rate (TmP/GFR), tubular reabsorption of phosphate (TRP), and fractional excretion of phosphorus (FEP)

- Change and percent change from baseline over time in serum bone turnover markers, including procollagen type 1 N-propeptide (PINP), carboxy-terminal cross-linked telopeptide of type I collagen (CTX), and bone-specific alkaline phosphatase (BALP)

4.4 Exploratory Efficacy Endpoints

The following exploratory efficacy endpoints will be examined:

- The number of active pseudofractures as defined by skeletal survey at baseline and the number and percentage of the baseline active pseudofractures which healed, partially healed, were unchanged or worsened at post-baseline visits
- The number of subjects with baseline active pseudofractures and the number of those subjects who have changes from baseline to healed, partially healed, unchanged and worsened at post-baseline visits
- Change from baseline over time in Brief Pain Inventory (BPI) Q3 – Worst Pain
- Change from baseline over time in BPI Pain Severity Score
- Change from baseline over time in Pain Interference scores
- Change from baseline over time in Brief Fatigue Inventory (BFI) Q3 – Worst Fatigue scores
- Change from baseline over time in BFI Global Fatigue Score, calculated by averaging all 9 items on the BFI

4.5 PK Endpoints

Serum KRN23 concentrations will be obtained from all subjects at time points reflecting peak and trough drug concentration.

4.6 Safety Endpoints

Safety will be evaluated by the incidence, frequency and severity of AEs and serious adverse events (SAEs), including clinically significant changes from baseline to scheduled time points in the following safety variables:

General safety variables include:

- Vital signs and weight
- Physical examinations
- Estimated glomerular filtration rate (eGFR)

- Chemistry, hematology, and urinalysis, including additional KRN23/XLH biochemical parameters of interest (creatinine, calcium, and intact parathyroid hormone [iPTH])
- Immunogenicity (human anti-human antibodies; HAHA)
- Concomitant medications

Ectopic Mineralization Safety Assessments:

- Renal ultrasound
- Echocardiogram (ECHO) and electrocardiogram (ECG)

5 DEFINITIONS AND DERIVED EFFICACY VARIABLES

5.1 Baseline

Baseline is defined as the last non-missing measurement taken prior to or on the first dose of Investigational Product (IP) administered in the study.

5.2 Duration of Exposure

Duration of exposure to IP in days is defined as the following:

For the primary analysis or other specified analysis before final analysis,

- The date at milestone visit (e.g. week 48) – first date of IP + 1 day for the subjects completing the corresponding milestone visit
- Last date of IP – first date of IP + 28 days for the subjects early discontinued

For final analysis:

- Last date of IP – first date of IP + 28 days

5.3 Study Day

Study Day 1 is the first date of IP.

- For visit date that is after Study Day 1, Study Day is calculated as the visit date – the first date of IP +1.
- For visit date that is prior to Study Day 1, Study Day is calculated as the first date of IP – the visit date.

5.4 Fractional Excretion of Phosphorus

Fractional excretion of phosphorus (FEP) is defined as $100\% \times (2\text{-hour urine phosphorus} \times \text{serum creatinine}) / (2\text{-hour urine creatinine} \times \text{serum phosphorus})$.

5.5 Iliac Crest Bone Biopsy

A bone biopsy of the iliac crest will be performed to assess OV/BV, O.Th, OS/BS, MLt as well as other parameters. Subjects will receive two courses of tetracycline (or demeclocycline) label prior to biopsy associated with the Baseline and Week 48 (or Early Termination if it occurs between the Week 24 and Week 48) visits. Bone biopsy of the trans-iliac crest will be performed by a physician trained and experienced in the procedure. Baseline bone biopsies will be qualitatively analyzed in real time to assess the presence of osteomalacia. If a subject is determined not to have osteomalacia at the time of the initial

biopsy, that subject will continue on study but will not undergo the second bone biopsy at Week 48/ET.

Primary and secondary efficacy endpoints derived from these assessments are provided in Section 8.8.

5.6 Brief Pain Inventory

The short-form Brief Pain Inventory (BPI) is an 11-question, self-reported, pain-specific questionnaire with a recall period of 24 hours that may allow a detailed characterization of the pain experienced by patients with XLH. The BPI will be administered at pre- and post-treatment time points as indicated in the Schedule of Events ([Appendix 2](#)) to assess pain severity and the impact of pain on daily functioning as measured by subject self-report.

The BPI endpoints to be analyzed are as follows:

- Worst pain, defined as the answer to question 3 (pain at its worst in the last 24 hours)
- Pain severity, defined as the average of questions 3 through 6
- Pain interference, defined as the average of questions 9A through 9G regarding the extent to which pain interfered with daily activities in the last 24 hours.

5.7 Brief Fatigue Inventory

The Brief Fatigue Inventory (BFI) is a self-reported questionnaire consisting of 9 items related to fatigue that are rated on a 0 to 10 numerical rating scale with a recall period of 24 hours. As with the BPI, two dimensions are measured: fatigue and the interference of fatigue on daily life (activity, mood, walking ability, work, relations with others, and enjoyment of life). The BFI will be administered at pre- and post-treatment time points as indicated in the Schedule of Events ([Appendix 3](#)) to assess fatigue severity and the impact of fatigue on daily functioning as measured by subject self-report.

The BFI endpoints to be analyzed are as follows:

- Worst fatigue, defined as the answer to question 3 (fatigue at its worst in the last 24 hours)
- BFI Global Fatigue score, defined as the average of all 9 items (questions 1 through 3 and questions 4A through 4F) on the BFI as recorded on the day of the study visit.

5.8 Targeted Radiography and Skeletal Survey

A radiographic skeletal survey will be conducted at baseline to assess healing or resolution of current pseudofractures, determine areas of osteomalacia and enthesopathy, and identify the number of pre-existing fractures/pseudofractures. Standard radiographs will be obtained of the chest, lateral spine, right and left hand/wrist, right and left humerus, right and left radius/ulna, right and left femur/pelvis, right and left tibia/fibula, and right and left foot.

During the 48-week long Open-Label Treatment Period, targeted radiography at locations identified by the skeletal survey will be taken at Weeks 12, 24, 36, and 48 to monitor frequency and healing of pseudofractures. During the Treatment Extension Period, targeted radiographs will only be taken at clinic visits following newly diagnosed fractures.

Post-baseline radiographs will be compared to baseline radiographs using a pre-defined list of abnormalities by a trained central reader who is blinded to subject data. Existing and new pseudofractures will be graded as not healed, partially healed, or fully healed.

5.9 Time-Adjusted Area Under the Curve (AUC)

[figure not shown]
The trapezoidal rule is a numerical method that approximates the value of a definite integral.

$$\int_a^b f(x)dx$$

Response versus time AUCs will be calculated using the trapezoidal rule. The formula for the area of a trapezoid is

$$Area = w \left(\frac{h_1 + h_2}{2} \right)$$

where w is the width of the trapezoid and h_1 and h_2 are the two heights as shown below

Each pair of consecutive response assessment times t_1 and t_2 form the width of a trapezoid with $w_1 = t_2 - t_1$. The heights h_1 and h_2 are the response values at times t_1 and t_2 , respectively. AUC is the sum of trapezoidal areas across specified time point.

$$\int_a^b f(x)dx \approx w_1 \left(\frac{h_1 + h_2}{2} \right) + w_2 \left(\frac{h_2 + h_3}{2} \right) + \dots + w_{n-1} \left(\frac{h_{n-1} + h_n}{2} \right)$$

AUC values can be normalized to time-adjusted AUCs by dividing AUC by the duration of time included in AUC calculation.

$$\text{Time-Adjusted AUC} = \frac{\text{AUC}}{\sum w_i}$$

5.10 Adverse Events To Monitor

Injection Site Reaction (ISR): Defined by preferred terms under the Medical Dictionary for Regulatory Activities (MedDRA) high-level term (HLT) “Injection site reaction”.

Immunogenicity AE: Defined using relevant PTs in the narrow SMQs for “Hypersensitivity”.

Hyperphosphataemia AE: Defined by using PTs: “Hyperphosphataemia”, “Blood phosphorus increased”.

Ectopic mineralization related AE: There is no available SMQ. Ectopic mineralization related AE is defined using a MedDRA search of ‘calcification’.

Restless leg syndrome AE: Defined by PTs “Restless legs syndrome”, “Restlessness”, “Akathisia”, “Sensory disturbance”, “Psychomotor hyperactivity”, “Limb discomfort”, “Neuromuscular pain”, “Formication”.

See search criteria in [Appendix 4](#).

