#### **7.5.3.11 Adverse Events**

All AEs will be recorded from the time the subject signs the informed consent through the final Safety Follow-up TC (as defined in Section 7.4.3.1). The determination, evaluation, reporting, and follow-up of AEs will be performed as outlined in Section 8.5. At each visit, subjects will be asked about any new or ongoing AEs since the previous visit. Assessments of AEs will occur at each visit to the investigational site and at all Home Health Visits.

Clinically significant changes from baseline in physical examination findings, vital signs, weight, clinical laboratory parameters, renal ultrasounds, eGFR, ECHO and ECGs will be recorded as AEs or SAEs, if deemed appropriate by the investigator.

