#### **7.6.5 Safety Analyses**

Safety will be evaluated by the incidence, frequency and severity of AEs and SAEs, including clinically significant changes from baseline to scheduled time points in vital signs and weight, physical examinations, eGFR, chemistry, hematology, urinalysis, immunogenicity, and concomitant medications. Additional safety parameters to assess the risk of ectopic mineralization include renal ultrasound, ECHO and ECG findings. Safety analysis will be performed using the safety analysis set.

All AEs will be coded using the Medical Dictionary for Regulatory Activities (MedDRA). The incidence and frequency of AEs will be summarized by System Organ Class, Preferred Term, relationship to study drug, and severity. All reported AEs with onset during the treatment (i.e. treatment-emergent AEs) will be included in the analysis. For each AE, the percentage of subjects who experienced at least 1 occurrence of the given event will be summarized. Special attention will be given to those subjects who died, discontinued treatment due to an AE, or experienced a SAE (e.g. summaries, listings, and narrative preparation may be provided, as appropriate).

Clinical laboratory data will be summarized by the type of laboratory test. Reference ranges and markedly abnormal results (specified in the SAP) will be used in the summary of laboratory data. The frequency and percentage of subjects who experience abnormal clinical laboratory results (i.e. outside of reference ranges) and/or clinically significant abnormalities

(as determined by the investigator) will be presented for each clinical laboratory measurement.

The SAP will provide additional details on the planned safety analyses.

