3 STUDY DESIGN

3.1 Overall Study Design and Plan

This is a Phase 3 open-label, single-arm, multicenter study to establish the effects of KRN23 on bone quality and osteomalacia associated with XLH. A total of 14 adult subjects with a diagnosis of XLH supported by typical clinical and biochemical features who have not received oral phosphate and vitamin D therapy in the past two years have been enrolled. To ensure a level of gender balance, at least 3 subjects of each sex have been enrolled. Iliac crest bone biopsies will be performed at baseline and 48 weeks. Baseline histologic and histomorphometric assessments of the bone biopsy specimens will be performed as each biopsy is completed to assess sample quality and confirm the presence of osteomalacia in at least 8 subjects. If a subject is determined not to have osteomalacia at the time of the initial biopsy, that subject will continue on study but will not undergo the second bone biopsy procedure at Week 48. All other assessments will be completed as scheduled. The goal of the study is to assess changes in bone quality. Histologic and histomorphometric evaluation of iliac crest bone biopsies will be supported by changes in serum phosphorus and biochemical markers of bone turnover and additional PD markers associated with FGF23-mediated processes. Pseudofractures and PROs will provide additional information on KRN23 efficacy. Safety, immunogenicity, and PK of KRN23 will also be evaluated.

KRN23 will be administered via subcutaneous (SC) injections monthly (Q4W, 28 days) for 48 weeks. Subjects who complete the 48 weeks of the Open-Label Treatment Period will then continue into an additional 48-week Treatment Extension Period. A Safety Follow-up Phone Call will be conducted 12 weeks (\pm 5 days) after the last dose of study drug.

All subjects will receive 1.0 mg/kg KRN23 monthly (Q4W, 28 days), rounded to the nearest 10 mg. The amount of drug administered will be calculated based on baseline weight and a 1.0 mg/kg KRN23 dose level (rounded to the nearest 10 mg) up to a maximum dose of 90 mg. The dose will remain fixed for the duration of the study, provided serum phosphorous levels do not exceed 5.0 mg/dL (1.61 mmol/L) at any time or 4.5 mg/dL (1.45 mmol/L) on two occasions. The dose will be recalculated if body weight changes by more than 20% from the baseline measurement.

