7.2 Unscheduled or Early Termination Visits

For an unscheduled visit occurring after the first dose date of IP, the unscheduled visit will be mapped into the closest post-baseline study scheduled visit for the assessment based on the study day of the unscheduled visit, and the target study day of the scheduled visit of the assessment in the protocol. If the unscheduled visit has the equal distance to the 2 study scheduled visits, it will be mapped to the later one.

The unscheduled visit will be only mapped to the study visit within each study period during which it occurs. If an unscheduled visit occurs during the Open-Label Treatment Period (from the first dose date to the dose date at week 48), it should be mapped to the study visit in the Open-Label Treatment Period. If an unscheduled visit occurs after the dose date at week 48 and in the Treatment Extension Period, it should be mapped to the study visit in the Treatment Extension Period.

When there is more than one measurement mapped to the same scheduled visit (including the original measurement taken from the scheduled visit), the measurement taken on the scheduled visit will be used if it is not missing, otherwise the one closest to the target day will be used. If more than one visit has the equal distance to the target day then the later one will be used. If more than one measurement is collected on the same day, use the time or the sequence number to select the latest record. For listings and shift tables, all data points will be included.

Early termination visit will follow the same rule for unscheduled visit as described above.

The bone biopsy taken in the early termination visit will not be mapped to the study scheduled visit as the bone biopsy will be only taken either on week 48 or at the early termination visit post-baseline used in the analysis.

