8.8.2 Adverse Events

Reported adverse event (AE) terms are coded to MedDRA (version 18.1). All reported events will appear in AE listings, however only TEAEs will be summarized. TEAEs are defined as AEs occurring or worsened in severity on or after the first dose date of IP.

The following AEs will be summarized at each milestone analysis:

- All TEAEs
- Related TEAEs
- TEAE by severity
- Events to monitor:
 - Injection site reactions
 - Immunogenicity
 - Hyperphosphataemia
 - Ectopic mineralization
 - Restless legs syndrome
- Grade 3/4 TEAEs
- Serious TEAEs
- Serious related TEAEs
- TEAEs resulting in discontinuation
- Fatal TEAEs.

The incidence and frequency of AEs will be summarized by System Organ Class (SOC), Preferred Term (PT). Events to monitor will be summarized by PT. Injection site reactions (ISR) will be listed for PT, seriousness, severity, outcome, relationship to study drug, and onset time from IP administration.

Listings will be created for AEs which lead to death, discontinuation of treatment, and SAEs.

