8.8.4 Safety Lab Parameters

The descriptive statistics will be provided for lab safety parameters (chemistry, hematology, and urinalysis parameters, serum 25(OH)D, FGF23, lipase, amylase, eGFR). Observed values and change from baseline will be presented.

In addition, a shift table will be provided for amylase. The following categories will be used for serum amylase:

- No Grade
- Grade 1: >ULN to 1.5 x ULR
- Grade 2: >1.5 to 2 x ULR
- Grade 3: >2 to 5 x ULR
- Grade 4: > 5 x ULR

Individual and mean (\pm SE) over time plots may be presented for selected safety lab parameters.

Listings of the lab safety parameters will be provided.

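### Hyperphosphataemia events are counted only from reported AE terms, and the SAP plans no count of subjects whose serum phosphorus exceeds 4.5 or 5.0 mg/dL

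*SAP*

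**What the plan says.** **Event definition.** SAP section 5.10 lists hyperphosphataemia among the events to monitor ("Hyperphosphataemia AE: Defined by using PTs") and names two terms: Hyperphosphataemia and Blood phosphorus increased. SAP section 8.8.2 adds: "Events to monitor will be summarized by PT". Under protocol section 7.5.3.11, clinically significant laboratory changes "will be recorded as AEs or SAEs, if deemed appropriate by the investigator".

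**Laboratory summaries.** Protocol section 7.6.5 states: "The frequency and percentage of subjects who experience abnormal clinical laboratory results", together with investigator-judged clinically significant abnormalities, will be presented for each laboratory measurement. It leaves the limits for markedly abnormal results to the SAP. SAP section 8.8.4 plans observed values and changes from baseline, and then says that "a shift table will be provided for amylase". SAP section 8.9 gives phosphorus observed values and changes. SAP section 8.6.3.2 adds efficacy summaries, including the proportion above the lower limit of normal. None of these counts subjects above an upper limit.

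**Unscheduled values.** SAP section 7.2 maps an unscheduled result to the nearest scheduled visit. Where several results fall on one visit, the one from "the scheduled visit will be used if it is not missing, otherwise the one closest to the target day will be used". Listings and shift tables keep every data point.

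**Thresholds in use.** In SAP section 3.1 and protocol section 7.4.1 the dose stays fixed "provided serum phosphorous levels do not exceed 5.0 mg/dL (1.61 mmol/L) at any time", or 4.5 mg/dL on two occasions. Both sections foresee unscheduled phosphorus tests.

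**The concern.** The study manages dosing by laboratory thresholds, but its hyperphosphataemia table counts what investigators chose to report as an AE. A value above 4.5 mg/dL that is not reported is not an event in that table. The count would also not be comparable with the protocol's statement that no hyperphosphataemia, meaning a value above 4.5 mg/dL, was seen in the earlier study that supports the dose (section 7.4.3).

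Protocol section 5.2.2 links soft-tissue and organ mineralization in animals, including nephrocalcinosis, to prolonged and excessive serum phosphate. How many subjects went above the limits is therefore a basic safety result. As planned, the report could show no hyperphosphataemia events next to dose reductions made for high phosphorus.

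**Working it through.** The documents give no figure for this point, so the check traces where a high value can appear and then counts how often a peak depends on an unscheduled sample.

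**Step 1. Where a high post-baseline value appears**

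| Value | AE-term count (5.10, 8.8.2) | By-visit summary (7.2, 8.1) | Dosing summary (8.8.1) | Count of subjects above a limit |
|---|---|---|---|---|
| Scheduled, above 4.5 | Only if reported | Yes, reflected in the maximum | Only if above 5.0 or a second result above 4.5 | None planned |
| Unscheduled, above 5.0, or second above 4.5 | Only if reported | Only if the scheduled value is missing | Yes, if the dose rule is followed | None planned |
| Unscheduled, single, above 4.5 up to 5.0 | Only if reported | Only if the scheduled value is missing | No | None planned |

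When the scheduled value is present and no AE is reported, the last row reaches only a listing. The all-data-points rule for shift tables does not help, because no phosphorus shift table is planned.

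**Step 2. Cycles with a scheduled between-dose sample**

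Inputs: dosing every 4 weeks from Week 0; scheduled post-baseline phosphorus at Weeks 1, 2, 4, 6, 12, 14, 20, 21, 22, 24, 28, 36, 48, 60, 70, 72, 84, 94 and 96 (SAP Appendix 1, protocol Tables 2.2 and 2.3). Samples on dosing days are taken before the injection (table footnote 6).

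| Weeks | Cycles | With a between-dose sample | Sample weeks |
|---|---|---|---|
| 0-24 | 6 | 4 | 1 and 2; 6; 14; 21 and 22 |
| 24-48 | 6 | 0 | none |
| 48-96 | 12 | 2 | 70; 94 |
| Total | 24 | 6 | |

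In the other 24 - 6 = 18 cycles, only an unscheduled sample can show a mid-cycle peak. Protocol section 7.4.3 reports that phosphorus fell towards the end of each dose interval, so a pre-dose sample tends to miss the peak.

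**Step 3. The mapping rule applied to those 18 cycles**

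Assume one unscheduled sample 2 weeks after each dose, and map it to the nearest scheduled phosphorus visit in the same period, taking the later visit if tied:

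- Weeks 10, 18, 26, 30, 34, 38, 42 and 46 map to Weeks 12, 20, 28, 28, 36, 36, 48 and 48.
- Weeks 50, 54, 58 and 62 map to Week 60; Week 74 maps to Week 72; Weeks 78, 82 and 86 map to Week 84.
- Weeks 66 and 90 map to Weeks 70 and 94.

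All 18 land on a different scheduled week. In 8 + 4 + 1 + 3 = 16 of the 18, that week is a dosing visit with a pre-dose sample. In each case the unscheduled value is left out of the by-visit summary if the scheduled value exists, and can be used if it does not.

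**Step 4. Weight of one uncounted subject**

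SAP section 3.1 gives 14 enrolled. The 95% intervals use the Wilson method, which the SAP names for its key secondary endpoint. For 0 of n the upper limit is z²/(n + z²) = 3.84/(14 + 3.84) = 21.5%.

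| Subjects of 14 | Incidence | Wilson 95% CI |
|---|---|---|
| 0 | 0% | 0 to 21.5% |
| 1 | 7.1% | 1.3 to 31.5% |
| 2 | 14.3% | 4.0 to 39.9% |

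The documents state no exceedance rate. Under assumed subject-level risks of 2%, 5% and 10%, the chance of at least one case, 1 - (1 - p)^14, is 25%, 51% and 77%.

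**The case against.** The best defence is that most high values are visible somewhere.

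- **Dose adjustments.** A value above 5.0 mg/dL, or a second above 4.5, leads to a dose adjustment, and SAP section 8.8.1 summarizes adjusted subjects with reasons. This stands. A reader might infer that an unscheduled value above 5.0 would appear only in a listing. If the dose rule is followed, that is wrong.
- **Missing scheduled values.** A reader might also infer that unscheduled peaks never reach a summary table. SAP section 7.2 does not support this, because it uses them when the scheduled value is missing.
- **Maxima.** SAP section 8.1 requires the maximum for continuous variables, so a scheduled high would show. This stands, but a maximum does not say how many subjects were high, or whether one subject was high twice.
- **Precedence.** SAP section 1 gives the SAP priority where the documents are inconsistent. Silence is not inconsistency, so the commitment in protocol section 7.6.5 is unimplemented, not cancelled.
- **Purpose of section 5.10.** Defining an AE group by preferred terms is normal, and one of the two terms is a laboratory term. The gap lies in sections 8.8.4 and 8.9.
- **Low expected frequency.** In the earlier studies no subject approached 4.5 mg/dL and the largest rise was about 1 mg/dL. From an entry value below 2.5 mg/dL, that suggests peaks below about 3.5 mg/dL. Nephrocalcinosis and cardiac mineralization have their own analyses, and the internal safety team reviews grade 2 or higher laboratory values. These lower the likely impact, but they do not give the reported count.

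**Conclusion.** The point holds in a limited form. The only planned count of hyperphosphataemia depends on AE reporting, no table counts subjects above 4.5 or 5.0 mg/dL, and the abnormal-result frequencies promised in protocol section 7.6.5 are not carried into the SAP. The value lost from every table is a narrow one: a single unscheduled result above 4.5 and up to 5.0 mg/dL, not reported as an AE, at a visit where the scheduled value is present. Other exceedances leave a trace in a maximum or in the dosing summary, but are still not counted against a threshold.

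The size is 7.1 percentage points per uncounted subject. The number of such subjects is unknown and may be zero. This rests on all 14 enrolled subjects being in the safety set, the visit schedule being kept, and, for the mapping, unscheduled samples falling about 2 weeks after a dose.

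**What to change.** In SAP section 8.8.4 or 8.9, add the number and percentage of subjects with any post-baseline serum phosphorus above 4.5 mg/dL, above 4.5 mg/dL on two occasions, and above 5.0 mg/dL. Use all scheduled and unscheduled values, regardless of the visit mapping in section 7.2, and state in a footnote how two occasions are counted. Show these rows beside the AE-term count so that any difference is visible.

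Also add the reference-range abnormality table that protocol section 7.6.5 promises, with the markedly abnormal limits that it leaves to the SAP.

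The cost is SAP wording and one or two tables from data already collected. No dosing or clinical rule changes. The reported incidence may look less favourable, by 7.1 percentage points for each additional subject counted.
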